8.8. Serious Adverse Events Exempt from Expedited Reporting by the Sponsor

All adverse events meeting SAE criteria (see [Section 8.4.1](#) above) must be reported to the Sponsor within 24 hours of when the site is notified of the event. The following refers to Sponsor processing of SAEs, but does not impact Investigator responsibilities for reporting of any SAE.

Potential pre-specified cardiovascular SAEs will be submitted for adjudication to an independent EAC (see [Section 7.6.1](#) for details).

The following potential cardiovascular SAEs will not be subject to expedited reporting by the Sponsor, even if reported as related to investigational product by the Investigator, unless and until the event is reviewed by the EAC and found not to meet the specified criteria in the EAC charter for that event type:

1. Cardiovascular deaths.

2. Non-fatal myocardial infarction; hospitalization for chest pain or to rule out myocardial infarction, or other hospitalization due to suspected myocardial ischemia where myocardial infarction needs to be ruled out.
3. Non-fatal stroke; TIA, reversible ischemic neurologic deficit (RIND) or other acute ischemic cerebrovascular event where stroke needs to be ruled out.
4. Hospitalization for unstable angina.

As noted above, SAEs that are confirmed by the EAC as one of the pre-specified cardiovascular endpoints (ie, cardiovascular death, non-fatal myocardial infarction, non-fatal stroke, and hospitalization for unstable angina) in the meta-analysis of cardiovascular safety will not be subject to expedited reporting by the Sponsor to Investigators, Ethics Committees/IRBs and regulatory agencies, regardless of causality. Note that all SAEs, including confirmed adjudicated cardiovascular events, will be reviewed and monitored by an E-DMC unblinded to treatment as part of the overall assessment of safety for ertugliflozin. Based upon their regular review of unblinded safety results, the E-DMC is empowered by the E-DMC charter to make recommendations with regard to trial conduct to assure the continuing appropriate safety of the subjects participating in the study.

If an event submitted for adjudication is determined by the EAC not to meet the endpoint criteria (for the pre-specified events of cardiovascular death, non-fatal myocardial infarction, non-fatal stroke, or hospitalization for unstable angina) in the EAC charter, the event will then be subject to expedited reporting (as appropriate, based upon Investigator assessment of drug relationship). The SAE awareness date in this instance is identified as the date that Pfizer or designee receives notification from the EAC that the event does not meet the endpoint criteria.

9. DATA ANALYSIS/STATISTICAL METHODS

All efficacy and safety analyses will be performed for the overall study population, as well as for the China subpopulation using the analysis methods described in [Sections 9.2 and 9.3](#).

Detailed methodology for summary and statistical analyses of the data collected in this trial will be documented in a Statistical Analysis Plan (SAP), which will be maintained by the sponsor. This document may modify the plans outlined in the protocol; however, any major modifications of the primary endpoint definition and/or its analysis will also be reflected in a protocol amendment.

9.1. Sample Size Determination

The sample size determination is based on the primary endpoint, reduction in HbA1c from Baseline to Week 26, within the subjects enrolled from China. Assuming a standard deviation (SD) of 1.0%,¹¹⁻¹⁸ a sample size of 105 subjects from China per group (total of 315 subjects from China) provides approximately 95% power to detect a difference in HbA1c of 0.5% between each ertugliflozin dose and placebo (and approximately 90% power for detecting this difference for both doses vs. placebo) using a two-sided 0.05 alpha level test. To control the overall Type I error rate at 0.05 within each population (overall study

population and the China subpopulation) a sequential testing approach will be used across the primary and secondary efficacy endpoints for which hypotheses will be tested, and for the two doses of ertugliflozin. Assuming a drop-out rate of 20% at Week 26 [(ie, either subjects who discontinue from the study, discontinue administration of IP (Investigational Product) or subjects who take rescue medication and are censored], approximately 396 subjects from China (132 per group) will be randomized. Additionally, this study will have approximately 99 subjects from at least two other Asian countries.

The total sample size for this study is approximately 495 randomized subjects.

9.2. Efficacy Analysis

The primary analysis population for efficacy analyses will be the Full Analysis Set (FAS), which is defined separately for each analysis endpoint to include all randomized subjects who have received at least one dose of investigational product and have at least one measurement of the respective endpoint at any time during the trial including baseline and post-baseline time points. Post-glycemic rescue therapy data from subjects who receive rescue therapy prior to Week 26, as well as post-bariatric surgery data will be censored from efficacy analyses.

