5.6. Glycemic Rescue Therapy

Subjects will be prescribed open-label glycemic rescue therapy with glimepiride with initial dose and titration managed according to physician judgment, if they meet specific, progressively more stringent, glycemic thresholds based on a **repeated, confirmed** FPG measured by the **central lab** according to the directions below:

Table 4. Glycemic Thresholds

After Randomization (Day 1) through Week 6:	FPG >270 mg/dL (15.0 mmol/L)
After Week 6 through Week 12:	FPG >240 mg/dL (13.3 mmol/L)
After Week 12 through Week 26:	FPG >200 mg/dL (11.1 mmol/L)

Subjects who meet the glycemic rescue thresholds detailed in Table 4 should have the repeat FPG measurement performed as early as possible (within 7 days following the receipt of test results).

Glycemic rescue therapy with glimepiride must be initiated at a rescue visit which is either a scheduled or an unscheduled visit at the investigational site, and not by a telephone visit. The investigator will determine initial dose and manage glimepiride titration as clinically appropriate and consistent with the country-specific product label. At the rescue visit, immediately prior to initiation of glycemic rescue therapy, subjects meeting rescue criteria must undergo the procedures described in [Section 6.5](#).

Subjects requiring glycemic rescue therapy are to remain in the trial (unless they meet discontinuation criteria) up to their trial completion by Week 26 (or Early Termination), and will continue to receive background metformin (same dose and regimen) and blinded investigational product (ertugliflozin/placebo).

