6.3.5. Week 26 (Visit 8) – Final Study Visit / Early Termination Visit

At Week 26 \pm 7 days relative to Day 1 (V4), subjects will return to the site after a minimum **10-hour fast** (except water) for V8. At this visit (or early termination visit), the following procedures will be completed:

- Contact IVRS.
- Assess treatment compliance with investigational product.
- Review and update concomitant medications since last visit.
- Measure body weight in duplicate [refer to [Section 7.2](#)].
- Obtain supine, single, standard, 12-lead ECG [refer to [Section 7.4.4](#)].
- Collect triplicate measurements of sitting blood pressure and pulse rate [refer to [Section 7.4.2](#)].
- Conduct brief physical examination which includes assessment of heart, lungs, abdomen and extremities.
- Obtain duplicate orthostatic blood pressure and pulse rate measurement (supine \rightarrow standing [refer to [7.4.3](#)].
- Conduct inquiry about any spontaneously reported AEs by asking the subjects to respond to a non-leading question such as “how do you feel?” Assess potential clinical events for adjudication [refer to [Section 7.6](#)].
- Review self-monitoring blood glucose and Hypoglycemia Assessment Logs completed by the subject [refer to [Section 7.4.6](#)].
- Diet and exercise monitoring (see [Section 6.1.2](#)).

- Obtain blood and urine specimens for clinical laboratory tests [refer to [Section 7.4.1](#)] of:
 - Hematology, chemistry, urinalysis, urinary albumin/creatinine ratio, urine pregnancy test (for women of childbearing potential) [refer to [Section 7.1](#)], lipid panel, HbA1c, FPG;
 - Pharmacokinetics of ertugliflozin (on a plasma sample) [refer to [Section 7.5.1](#)] including collection of date/time of blood draw and date/time of last dose of investigational product. PK sample is to be collected approximately 24 hr following the prior day's dose.

Subjects, who discontinue from the trial prematurely, should be reminded that they will be contacted via telephone by the Investigator/qualified designee according to the same schedule as if they were still taking investigational product and will be asked to return for a visit at the Week 26 visit unless they withdraw consent per [Section 6.6](#).

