Subjects who are discontinued from investigational product but agree to continue to participate in the trial by providing follow-up information can have medical and diabetes management by their managing physician or Investigator, as appropriate. These subjects may initiate any other therapy as needed (previously prohibited medications may be used). After discontinuation of investigational product, Pfizer or its designee will continue to reimburse/supply (as specified in [Section 5.6.1](#)), glimepiride (for those rescued) until Week 26. The Investigator should ensure that the subject has enough open-label rescue medication until the next scheduled in clinic visit (if applicable). Procurement of any other AHAs is the responsibility of the subject.

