If a subject discontinues investigational product, he/she should complete all Early Termination Visit procedures as described in [Section 6.3.5](#) and listed in [Schedule of Activities](#). Unless the consent to follow the subject is specifically withdrawn, a subject will be contacted via telephone by the Investigator/qualified designee according to the same schedule as if he/she were still taking investigational product and will be asked to return for a visit at Week 26. Such subjects may initiate other AHA therapy as indicated (prohibited medications described in [Section 5.5](#) will not apply to these subjects.)

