9.2.1. Analysis of Primary Endpoint

The primary endpoint of HbA1c will be analyzed using a constrained longitudinal data analysis (cLDA) model with the following terms:

- Country (categorical) (Applicable only for the analyses of the overall study population)
- Treatment (categorical),
- Visit (categorical),
- Treatment by visit interaction (categorical),
- AHA status at study entry (binary),
- Baseline eGFR (continuous) Values above 120 mL/min per 1.73 m² will be set to 120 mL/min per 1.73 m².

This model assumes a common mean across treatment groups at baseline and a different mean for each treatment at each of the post-baseline time points. In this model, the response vector consists of baseline and the values observed at each post-baseline time point.²⁰ Time is treated as a categorical variable so that no restriction is imposed on the trajectory of the means over time. No explicit imputation of missing assessments will be performed. The treatment difference between each dose of ertugliflozin and placebo in terms of mean change from baseline at the primary time point of Week 26 will be estimated and tested from this model using least-squares means and 95% confidence intervals. The two-sided p-value will also be provided for testing the significance of the difference between treatment groups. An

unstructured covariance matrix will be used to model the correlation among repeated measurements. The Kenward-Roger adjustment will be used with restricted (or residual) maximum likelihood (REML) to make proper statistical inference. Methods to address the potential issue of large differences in sample size from different countries will be described in the SAP.

Sensitivity analyses will be performed to assess the robustness of the primary model. ANCOVA will be conducted utilizing the last observation carried forward as the dependent variable and including fixed factors for country (categorical), treatment (categorical), baseline HbA1c (continuous), AHA status at study entry (binary), baseline eGFR (continuous) (eGFR values above 120 mL/min per 1.73 m² will be set to 120 mL/min per 1.73 m²). A per protocol analysis will also be pre-specified in the statistical analysis plan. Descriptive and graphical summaries by treatment group and time point will also be presented. The models utilized for the China subpopulation will not include country as a term.

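### The protocol conflicts on whether a Week 26 visit follows stopping of investigational product, and Section 9.2 does not list HbA1c taken after another glucose-lowering drug among the values it censors

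*Combined protocol and SAP*

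**What the plan says.** **Censoring.** Section 9.2 removes two kinds of efficacy data, those after glycemic rescue and those after bariatric surgery: "rescue therapy prior to Week 26, as well as post-bariatric surgery data will be censored from efficacy analyses". The synopsis names only the first. Rescue has a specific meaning in Section 5.6: "Subjects will be prescribed open-label glycemic rescue therapy with glimepiride", triggered by a confirmed central-laboratory FPG above a threshold.

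**Model.** Section 9.2.1 fits a constrained longitudinal model in which "the response vector consists of baseline and the values observed at each post-baseline time point". It states no restriction to on-treatment values and no cut-off after the last dose.

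**Other therapy after IP.** Section 6.6 says of subjects who stop IP but stay in follow-up: "These subjects may initiate any other therapy as needed (previously prohibited medications may be used"). Section 6.6.1 likewise lets them start other AHAs.

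**Follow-up after IP.** The passages differ:
- Section 6.6 gives an early termination visit, a 14-day call, then telephone contacts to Week 26 and no other scheduled procedures. Further on, it allows either clinic visits or contact without them.
- Section 6.6.1 says that a subject who stops IP "will be asked to return for a visit at Week 26".
- Section 6.3.5 says that subjects who discontinue from the trial "will be asked to return for a visit at the Week 26 visit unless they withdraw consent".
- Section 7.1 repeats the return visit for pregnancy.
- The early termination footnote to the Schedule of Activities mentions only that visit and telephone contact.

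**Deferral.** Section 9 sends detailed methods to a SAP: "This document may modify the plans outlined in the protocol". Section 9.2.1 adds: "A per protocol analysis will also be pre-specified in the statistical analysis plan".

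**The concern.** Two things go wrong together. First, a site that reads Section 6.6 will telephone a subject who has stopped IP, and a site that reads Section 6.6.1 will ask the same subject to come in. Whether a Week 26 HbA1c exists then depends on which passage the site applied and what the subject preferred. A value that was not drawn cannot be recovered later.

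Second, where a value is drawn, the stated censoring list is uneven. HbA1c after added glimepiride is removed. HbA1c after any other agent, started once IP has been stopped, is not on the list. The sample size section counts IP discontinuers as drop-outs, which sits badly with their later values being eligible for the primary model. At stake is a clear definition of which values the primary comparison uses in a trial meant to support registration.

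**Working it through.** **1. The plan's own figures (Section 9.1).** Inputs: SD 1.0, difference 0.5, two-sided 0.05, 105 evaluable Chinese subjects per group, 20% drop-out.
- Per dose: 0.5/√(2/105) = 3.623; 3.623 − 1.960 = 1.663; Φ(1.663) = 0.952. The plan says about 95%.
- Both doses, with correlation 0.5 from the shared placebo arm: 0.915. The plan says about 90%.
- Randomized: 105/0.8 = 131.25, rounded up to 132; 3 × 132 = 396; 396 + 99 = 495.

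All reproduce.

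**2. Follow-up passages compared.** Sections 6.6 and 6.6.1 deal with the same event, stopping IP, and cannot both be followed as written. Section 6.3.5 is a weaker partner, because it speaks of discontinuing from the trial. None of these passages lists the procedures for the return visit. That HbA1c would be drawn there is an inference from the Week 26 procedures in Section 6.3.5, and the schedule uses one shared column for Week 26 and early termination.

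**3. Which post-IP values the censoring rule reaches.**
- IP stopped after failed rescue or for glimepiride intolerance while on rescue: already censored as post-rescue.
- IP stopped for bariatric surgery: already censored.
- IP stopped by an un-rescued subject who then starts another AHA: meets neither condition.

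Bariatric surgery is itself a reason to stop IP (Section 6.6.1, item 9), so Section 9.2 foresees some post-IP data but excludes only one kind.

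**4. Consistency with sizing.** Sections 3 and 9.1 include stopping IP in the 20% allowance. In both, the words about censoring attach to rescue, so neither gives an analysis rule for values after IP.

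**5. Illustration of size.** The documents do not split the 20% or give an effect after IP. Assume that a fraction f of randomized subjects per arm, equal across arms, stops IP un-rescued, starts another AHA and has a Week 26 HbA1c. Let r be the share of the drug effect that remains in them. For China:
- n0 = 0.8 × 132 = 105.6; m = f × 132; n = n0 + m; s = m/n
- effect = 0.5 × (1 − s(1 − r)); power = Φ(effect/√(2/n) − 1.96)

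Without such subjects (n = 105.6), power is 0.953 per dose and 0.917 for both.

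| f | m | n | effect, r = 0 | per dose | both | effect, r = 0.5 | per dose | both |
|---|---|---|---|---|---|---|---|---|
| 4% | 5.3 | 110.9 | 0.476 | 0.944 | 0.902 | 0.488 | 0.953 | 0.917 |
| 7% | 9.2 | 114.8 | 0.460 | 0.936 | 0.890 | 0.480 | 0.953 | 0.918 |
| 10% | 13.2 | 118.8 | 0.444 | 0.929 | 0.877 | 0.472 | 0.954 | 0.918 |

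Power equals that of n0 alone when r is 0.494, 0.490 and 0.485 respectively. In the overall population (165 per arm, n0 = 132), per-dose power is 0.982 without such subjects. With r = 0 it is 0.978 at f = 4% and 0.969 at f = 10%; with r = 0.5 it is 0.982 and 0.983.

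**The case against.** The strongest reply is that the SAP is not in the supplied text. Section 9 sends detailed methods there and Section 9.2.1 sends the per-protocol analysis there, so a rule for values after IP may exist. This stands: the protocol section can be called silent, but the trial's plan cannot. It does not answer the visit conflict, because sites work from the protocol.

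It can also be said that the plan expects no Week 26 efficacy data after IP is stopped. Sections 3 and 9.1 count these subjects as drop-outs, and Section 6.6 and the schedule footnote describe telephone contact. That is a fair reading of those passages, but Section 6.6.1 says otherwise. A return visit without efficacy measures would reconcile them, though no passage says so.

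Three stronger readings are tempting and not supported. A reader might take the response-vector sentence in Section 9.2.1 as an instruction to include every value. Its evident purpose is to explain that baseline is treated as a response, so the argument rests on the absence of an exclusion. A reader might take the power table as the effect of the other AHAs. It models loss of drug effect only, and r = 0 could arise with no AHA at all. A reader might also take 4% to 10% as an estimate. It is an assumption, and its upper end is half of an allowance that also covers study withdrawals and rescues.

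Finally, rescued subjects stay on IP and these subjects do not, so keeping their values can be defended. What is needed is a stated choice.

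**Conclusion.** The point holds as a minor one. The firm part is the conflict between Sections 6.6 and 6.6.1 over what happens at Week 26 after IP is stopped. The conditional part is that, if HbA1c is then collected and the SAP adds nothing, Section 9.2 leaves in values taken after another AHA while removing those taken after glimepiride.

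The number of subjects affected is unknown. Under the assumptions above, the expected China difference falls from 0.50 to between 0.48 and 0.44 with no effect remaining. Per-dose power is then 94.4% to 92.9%, and power for both doses is 90.2% to 87.7% against a stated figure of about 90%. With half the effect remaining, power is unchanged.

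A reader might infer that the trial is underpowered or that superiority could be falsely claimed. Neither follows: the sample size arithmetic is correct, and in these scenarios the difference moves toward zero.

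**What to change.** 1. Reconcile Section 6.6 with Section 6.6.1, and align Sections 6.3.5 and 7.1 and the Schedule of Activities footnote, so that one rule says whether a Week 26 visit takes place after IP is stopped and whether HbA1c is drawn at it.
2. In Section 9.2, before unblinding, apply the existing rescue-censoring logic to efficacy values after the start of any non-protocol AHA, or confirm that the SAP already does so.
3. Add a supplementary analysis of all collected values regardless of rescue or IP discontinuation, so that the influence of the choice can be seen.

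The cost is two or three sentences in Section 9.2 and the SAP plus the wording alignment, with no extra patients. If a visit is confirmed, discontinuers who agree to return have one clinic visit. The downside is that a few values leave the primary model (at most about 13 of 132 per arm in China under the assumed range), with slightly more reliance on its missing-data assumption.

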9.2.1. Analysis of Primary Endpoint

The primary endpoint of HbA1c will be analyzed using a constrained longitudinal data analysis (cLDA) model with the following terms:

- Country (categorical) (Applicable only for the analyses of the overall study population)
- Treatment (categorical),
- Visit (categorical),
- Treatment by visit interaction (categorical),
- AHA status at study entry (binary),
- Baseline eGFR (continuous) Values above 120 mL/min per 1.73 m² will be set to 120 mL/min per 1.73 m².

This model assumes a common mean across treatment groups at baseline and a different mean for each treatment at each of the post-baseline time points. In this model, the response vector consists of baseline and the values observed at each post-baseline time point.²⁰ Time is treated as a categorical variable so that no restriction is imposed on the trajectory of the means over time. No explicit imputation of missing assessments will be performed. The treatment difference between each dose of ertugliflozin and placebo in terms of mean change from baseline at the primary time point of Week 26 will be estimated and tested from this model using least-squares means and 95% confidence intervals. The two-sided p-value will also be provided for testing the significance of the difference between treatment groups. An

unstructured covariance matrix will be used to model the correlation among repeated measurements. The Kenward-Roger adjustment will be used with restricted (or residual) maximum likelihood (REML) to make proper statistical inference. Methods to address the potential issue of large differences in sample size from different countries will be described in the SAP.

Sensitivity analyses will be performed to assess the robustness of the primary model. ANCOVA will be conducted utilizing the last observation carried forward as the dependent variable and including fixed factors for country (categorical), treatment (categorical), baseline HbA1c (continuous), AHA status at study entry (binary), baseline eGFR (continuous) (eGFR values above 120 mL/min per 1.73 m² will be set to 120 mL/min per 1.73 m²). A per protocol analysis will also be pre-specified in the statistical analysis plan. Descriptive and graphical summaries by treatment group and time point will also be presented. The models utilized for the China subpopulation will not include country as a term.

The two primary hypotheses, comparisons of each ertugliflozin dose to placebo will be tested sequentially to control the overall Type I error rate at 0.05 within each population (the overall study population, and China subpopulation) (see below for sequence of testing for the overall population and the China subpopulation). Within each of these two populations, the 15 mg dose will be tested first, and the 5 mg dose will be tested if and only if a statistically significant result is achieved for 15 mg.

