The primary endpoint of HbA1c will be analyzed by fitting a constrained longitudinal data analysis model with terms for country (China, Other), treatment, visit, treatment by visit interaction, AHA status at study entry (binary) and Baseline eGFR (estimated glomerular filtration rate). Least-squares means and 95% confidence intervals will be used to estimate the treatment effect (difference between ertugliflozin and placebo) at the primary time point of Week 26. The two-sided p-value will also be provided for testing the significance of the difference between treatment groups. The two primary hypotheses, comparisons of each ertugliflozin dose to placebo, will be tested sequentially to control the overall Type I error rate at 0.05 within each population (overall study population and China subpopulation). Within each of these two populations, the 15 mg dose will be tested first, and the 5 mg dose will be tested if and only if a statistically significant result is achieved for 15 mg. The model utilized for the China subpopulation will not include country as a term.

Analysis of Secondary Endpoints:

The proportion of subjects with an HbA1c <7.0% (53 mmol/mol) at Week 26 will be analyzed using a logistic regression model with terms for country (categorical), treatment (categorical), baseline HbA1c (continuous), AHA status at study entry (binary) and Baseline eGFR (continuous). Summary measures from the analysis will include the odds ratio, 95% confidence interval for the odds ratio, and p-value for the comparison of treatment groups.

The secondary endpoints of FPG, body weight, systolic blood pressure and diastolic blood pressure will be analyzed separately by fitting constrained longitudinal data analysis models similar to that used for the primary endpoint.

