1.5. Rationale for Study and Design

SGLT2 inhibitors lower blood glucose in an insulin-independent manner. Consequently, glucose lowering should be observed across the typical continuum of T2DM progression, ranging from subjects treated with diet and exercise alone to subjects receiving insulin.

This trial will assess the efficacy and safety of ertugliflozin added to the regimen of Asian subjects who have inadequate glycemic control on metformin monotherapy at or near maximally effective doses (ie, ≥ 1500 mg/day). Subjects already on metformin monotherapy at protocol-specified doses (≥ 1500 mg/day) for at least 8 weeks at S1 and who meet other enrollment criteria will go directly from S1 to S2/3 to enter the 2-week single-blind placebo run-in period.

In addition to subjects with inadequate control on metformin monotherapy at ≥ 1500 mg/day for ≥ 8 weeks, a broader range of subjects will be screened for the study. This includes subjects who have been on a stable dose of metformin ≥ 1500 mg/day for < 8 weeks, or metformin monotherapy at a dose < 1500 mg/day as well as subjects on metformin in combination with another allowable single AHA agent. Subjects not yet on a stable dose of metformin monotherapy ≥ 1500 mg/day for at least 8 weeks will enter a dose stable period at S2, so that they have received at least 8 weeks of a stable dose of metformin monotherapy prior to S3, where they will enter a 2 week single-blind placebo run-in period. Subjects receiving metformin and another allowable single AHA will discontinue the non-metformin AHA at S2 and enter a metformin monotherapy period (uptitrate metformin dose to ≥ 1500 mg/day if applicable) and reach a stable dose of ≥ 1500 mg/day for at least 8 weeks prior to S3. With the exception of subjects who at S1 are already receiving metformin monotherapy ≥ 1500 mg/day for at least 8 weeks, subjects on other allowable diabetes medications at S1 will have HbA1c measured again at S3 to determine if they qualify for enrollment.

The population to be enrolled in this study represents subjects appropriate to assess the primary and secondary objectives in the study.

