9.2.2. Analysis of Secondary Endpoints

The proportion of subjects with an HbA1c <7.0% (53 mmol/mol) at Week 26 will be analyzed using a logistic regression model with terms for country (categorical) (applicable only for the analyses of the overall study population), treatment (categorical), baseline HbA1c (continuous), AHA status at study entry, and baseline eGFR (continuous). Summary measures from the analysis will include the odds ratio, 95% confidence interval for the odds ratio, and p-value for the comparison of treatment groups.

The secondary endpoints of fasting plasma glucose, body weight, systolic blood pressure and diastolic blood pressure will be analyzed separately by fitting constrained longitudinal data analysis models similar to that used for the primary endpoint. Sitting blood pressure collected in triplicate will be used for assessment of blood pressure as a secondary endpoint.

For the overall study population, the secondary efficacy endpoints of FPG, proportion of subjects with an HbA1c <7.0%, body weight, systolic blood pressure and diastolic blood pressure will be tested for each ertugliflozin dose versus placebo using a multiple testing procedure that strongly controls the overall Type I error rate at 0.05. For the China subpopulation, due to smaller sample size, which limits power for other secondary endpoints, only FPG and body weight endpoints will be tested for each ertugliflozin dose versus placebo using a multiple testing procedure that strongly controls the Type I error rate at 0.05. Therefore, a step-down hierarchical, sequential testing approach will be used, as follows:

Order (for Overall Study population)	Order (for China subpopulation)*	Endpoint (Change from Baseline to Week 26**)	Arm Comparison
1	1	HbA1c	15 mg ertugliflozin arm to placebo
2	2	HbA1c	5 mg ertugliflozin arm to placebo
3	3	FPG	15 mg ertugliflozin arm to placebo
4	4	FPG	5 mg ertugliflozin arm to placebo
5	5	Body Weight	15 mg ertugliflozin arm to placebo
6	6	Body Weight	5 mg ertugliflozin arm to placebo
7	N/A	HbA1c <7.0% at Wk 26	15 mg ertugliflozin arm to placebo
8	N/A	HbA1c <7.0% at Wk 26	5 mg ertugliflozin arm to placebo
9	N/A	Systolic BP	15 mg ertugliflozin arm to placebo
10	N/A	Systolic BP	5 mg ertugliflozin arm to placebo
11	N/A	Diastolic BP	15 mg ertugliflozin arm to placebo
12	N/A	Diastolic BP	5 mg ertugliflozin arm to placebo

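### Does listing country, AHA status and eGFR only as main effects weaken the primary HbA1c model?

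*Combined protocol and SAP*

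**What the plan says.** Section 9.2.1 puts baseline HbA1c among the outcomes: "In this model, the response vector consists of baseline and the values observed at each post-baseline time point". It assumes a common baseline mean across arms and an unstructured covariance matrix. The synopsis gives the same list: "terms for country (China, Other), treatment, visit, treatment by visit interaction, AHA status at study entry (binary) and Baseline eGFR". The only interaction is treatment by visit. Country drops out of the China model.

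Section 9.2.1 also plans an ANCOVA on the last observation carried forward (LOCF), with country, treatment and "baseline HbA1c (continuous), AHA status at study entry (binary), baseline eGFR (continuous" among its terms. The stated purpose is general: "Sensitivity analyses will be performed to assess the robustness of the primary model". On country the section adds: "Methods to address the potential issue of large differences in sample size from different countries will be described in the SAP". Section 9 leaves detailed methodology to a separate SAP, whose text is not in the file.

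Section 9.2.2 says that FPG, body weight, systolic and diastolic blood pressure will be "analyzed separately by fitting constrained longitudinal data analysis models similar to that used for the primary endpoint".

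**The concern.** In an ordinary change-from-baseline model, a covariate main effect explains variation in change. In a cLDA it does not, because baseline is itself an outcome. A coefficient that is the same at every time point shifts baseline and Week 26 equally and disappears from the difference. A reader may conclude that the three covariates are there in name only and that the Week 26 interval is wider than it need be.

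The ANCOVA adds to the unease. It uses the same covariates without this constraint, so a gap between the two analyses could come from covariate form as well as from missing-data handling. At stake would be the precision of the primary contrast, the reading of the sensitivity analysis, and the same form carried into four secondary endpoints.

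**Working it through.** **1. The plan's own power.** Section 9.1 gives 105 per arm in China, a difference of 0.5 and two-sided alpha 0.05: "Assuming a standard deviation (SD) of 1.0" (per cent).

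SE = sqrt(2 x 1.0^2 / 105) = 0.1380. Power = Phi(0.5/0.1380 - 1.96) = Phi(1.66) = 95.2%. The stated figure reproduces. With the SD read as that of change, it takes no credit for adjustment by baseline or covariates.

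**2. The algebra.** For a covariate X with coefficient b, the modelled mean is mu_0 + bX at baseline and mu_t + tau_t + bX at visit t. The modelled mean change is mu_t - mu_0 + tau_t, so bX cancels. Randomisation still balances X across arms, so tau_t is not biased. In simulations with covariates explaining 0-20% of the variance of change, mean estimates lay between -0.48 and -0.52 for a true -0.5, and the main-effects and by-visit forms differed by at most 0.005.

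**3. Precision, before the cost of extra parameters.** Assumptions not in the documents: 40% of subjects on a second AHA at entry, equal correlation r between visits, and a covariate shift in change that is constant over the four post-baseline visits. Total SD of change is fixed at 1.0. The China share is 396/495 = 0.8.

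With shift d and five time points, the best common coefficient is 0.8d. This leaves -0.8d unexplained at baseline and +0.2d at later visits. Let V be the variance of change due to the covariates and s2 = (1 - V) / (2(1 - r)). Then:

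- S00 = s2 + 0.64V; S44 = s2 + 0.04V; S04 = r x s2 - 0.16V
- main effects only: S44 - S04^2/S00
- by visit: s2(1 - r^2)

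Moderate case: AHA shift 0.3, eGFR 0.1 per SD, country 0.2, r = 0.6.

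- V = 0.3^2 x 0.24 + 0.1^2 + 0.2^2 x 0.16 = 0.0216 + 0.0100 + 0.0064 = 0.0380
- s2 = 0.962/0.8 = 1.2025
- S00 = 1.2268; S44 = 1.2040; S04 = 0.7154
- main effects only: 1.2040 - 0.7154^2/1.2268 = 0.7868
- by visit: 1.2025 x 0.64 = 0.7696
- variance ratio: 0.7868/0.7696 = 1.022

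**4. Net of the extra parameters.** By-visit terms add 3 x 4 = 12 parameters (8 in the China model). Variance ratios, main-effects over by-visit, for the overall model with 20% dropout and r from 0.4 to 0.75 (below 1 means that by-visit terms lose precision):

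| Assumed shifts (AHA / eGFR per SD / country) | Ratio |
|---|---|
| none | 0.995-0.996 |
| 0.1 / 0.05 / 0.1 | 0.999 |
| 0.2 / 0.05 / 0.1 | 1.001-1.005 |
| 0.3 / 0.1 / 0.2 | 1.009-1.021 |
| 0.5 / 0.1 / 0.3 | 1.026-1.055 |
| 0.6 / 0.2 / 0.3 | 1.047-1.099 |

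With AHA status alone predictive, break-even is a shift of about 0.2 points (0.17-0.25 over the correlations).

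**5. What this means for the result.** In the 0.3 case at r = 0.6, the 95% half-width is 0.211 as listed and 0.209 by visit. For China, V = 0.0216 + 0.0100 = 0.0316, and the two residual variances are 0.7891 and 0.7747. With 105 per arm the SEs are 0.1226 and 0.1215, and power for 0.5 is 98.3% and 98.4%.

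**6. Which row is plausible.** On the second AHA, section 1.5 says: "Subjects receiving metformin and another allowable single AHA will discontinue the non-metformin AHA at S2 and enter a metformin monotherapy period". At least 8 stable weeks and the 2-week run-in (section 3) give about 10 weeks off the drug before Day 1. These subjects must also have HbA1c of 7.0-10.5% at S3 (section 4.1, criterion 3). Some of the washout effect may therefore already be in baseline. If half of each effect is there, the 0.3 case falls to 0.999-1.001 and the 0.6 case to 1.008-1.019. If all of it is, no gain remains.

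**7. The ANCOVA comparison.** With complete data, a by-visit cLDA gives the ANCOVA estimate to within 1e-9 or so. The SD of the difference between the main-effects cLDA and the ANCOVA was 0.005 (no effect), 0.010 (0.2 case), 0.016 (0.3 case) and 0.027 (0.6 case), against a contrast SE of about 0.10.

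**The case for a change.** The strongest case for a change is that by-visit terms need no new data, lose at most about half a per cent of variance, and could gain up to about 10% if the covariates predict change strongly. They would also make the LOCF comparison a test of missing-data handling alone. A separate calculation, calibrated so that the listed model has the planned 95.2% power, gives 97.2% if the covariates explain 20% of the variance of change. Section 9.2.2 leaves the covariate form of four secondary models just as open.

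The algebra and the difference in covariate form stand, and in a favourable case some precision is forgone. Three things keep this from being a fault.

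- The larger gains need an AHA shift of 0.5 or more, at least the full design effect, arising after about 10 weeks off the drug. The documents give no basis for choosing those rows over the rows with a loss or no gain.
- Section 9.2.1 promises only a check of robustness. A sensitivity analysis that varies covariate form as well as missing-data handling serves that aim, and the part due to covariate form is small against the SE.
- The listed covariates are not inert. In one simulated scenario, where they explained 10% of baseline variance and none of change, adding them as main effects cut the SE from 0.1237 to 0.1222.

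The separate SAP may also settle the form. No size can be given for FPG, weight or blood pressure, so the objection adds nothing firm there.

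**Conclusion.** The concern does not hold. The listed model is a valid, pre-specified analysis. Its main-effects form causes no bias and no loss of Type I error control, and the stated power reproduces at 95.2%. The alternative form ranges from a variance loss of about 0.4-0.5% to a gain of about 1-2% in the moderate case, and about 10% only at the extreme. Entering the terms might also count as a major modification of the primary analysis, which section 9 says would need a protocol amendment.

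These sizes rest on assumed AHA share, visit correlations and covariate shifts, none of which the documents give. The conclusion about validity does not depend on them. Reasonable statisticians could choose either form, and the plan needs no correction on this point.
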